7.1 Demographic and Baseline Characteristics

For the subjects in ITT1A and safety analysis sets, demographic information and Baseline values will be summarized by descriptive statistics. Categorical data will be summarized by number and percent; and quantitative data will be presented by n, mean, standard deviation, minimum value, median, and maximum value.

In general, continuous variables will be analyzed using analysis of variance (using SAS procedure 'PROC GLM') with treatment group as factor. Categorical variable will be analyzed using chi-square test or Fisher's exact test if $\geq 20\%$ of the cells have expected cell count < 5 .

The following demographic and Baseline values will be summarized.

Continuous Variables:

- Age (years)
- Body weight (kg)
- Height (cm)
- Body Mass Index (kg/m²)
- Blood Pressure (systolic/diastolic) (mmHg)
- Pulse (bpm)
- Respiratory Rate (RPM)
- Temperature (°C)
- IBDQ score
- Full Mayo score and its components (stool frequency, rectal bleeding, PGA, and endoscopy subscores)
- Partial Mayo score
- Adapted Mayo score
- hs-CRP (mg/L)
- Fecal Calprotectin (µg/g)
- Albumin (g/L)
- Short Form 36 Health Survey (SF-36) and its components
- European Quality of Life 5 Dimensions 5 Levels (EQ-5D-5L)
- Functional Assessment of Chronic Illness Therapy-Fatigue (FACIT-F)
- WPAI and its components
- Ulcerative Colitis Symptoms Questionnaire (UC-SQ)
- Disease duration

Categorical Variables:

- Sex (male, female)
- Race
- Ethnicity
- Baseline corticosteroid use (yes, no)

- Baseline immunosuppressant use (yes, no)
- Baseline aminosalicylates use (yes, no)
- Baseline anti-TNF use (yes, no)
- Baseline biologics use (yes, no)
- Baseline hs-CRP (≤ 5 mg/L and > 5 mg/L)
- Disease duration (≤ 3 years, > 3 years)
- Tobacco use (user, ex-user, never used, unknown)
- Alcohol use (drinker, ex-drinker, non-drinker, unknown)
- Disease extent (rectosigmoid, left-sided, extensive/pancolitis)
- Region (US, ex-US)

7.2 Medical History

The following medical history will be presented for ITT1A and safety analysis sets.

Medical and Surgical History: A complete medical and surgical history (which includes CD-onset date), history of tobacco and alcohol use, and TB history will be obtained from each subject during the Screening period. Medical history will be summarized using body system and condition/diagnosis by treatment group. No statistical tests will be performed.

Chest X-Ray Results: Number and percent of subjects with presence or absence of finding for the previous TB infection, calcified granulomas, Pleural scarring/thickening, and other findings will be presented by treatment group. No statistical tests will be performed.

TB Test Results: Results of PPD skin test, QuantiFERON-TB Gold test reported at screening visit will be summarized. Induration will be summarized descriptively using n, mean, standard deviation, minimum values, median, and maximum values. The frequency distribution of induration ≥ 5 and < 5 will be provided. QuantiFERON-TB tests will be described as positive or negative. Indeterminate QuantiFERON-TB test results will be repeated. If the second QuantiFERON-TB test is positive or indeterminate,

the final assessment will be considered positive. If the second QuantiFERON-TB test is negative, the final assessment will be considered negative. No statistical tests will be performed.

TB Prophylaxis: History of use of TB Prophylaxis or initiation of TB prophylaxis will be summarized.

ECG Results: ECG results at screening will be presented as frequency distribution showing results as Normal, Abnormal (Not clinically significant), Abnormal (Clinically significant) and Unable to evaluate/missing. No statistical tests will be performed.

7.3 Previous Treatment and Concomitant Medications

Based on generic medication names, these categories of medications used by subjects before and during the study will be summarized by number and percent for ITT1A and safety analysis sets for the treatment groups. No statistical tests will be performed.

The number and percent of subjects using corticosteroid, immunosuppressant, aminosalicylates, anti-TNF or biologics within past 90 days prior to the Baseline, and at the Baseline will be tabulated. In addition, the number and percent of subjects using UC-related antibiotics at Baseline, and biologic therapies at any time prior to Baseline will be tabulated.

8.0 Patient Disposition

Subject disposition will be presented for subjects in the ITT1A and safety analysis sets using the following information by treatment group:

- Number and percent of subjects in various analysis sets by treatment group and by investigator and/or site number
- Number and percent of subjects completing double-blind induction period and discontinuing on or before Week 8 visit of Substudy 1
- Subject disposition including the number and percent of subjects who prematurely discontinued Substudy 1 by primary reason and by any reason

Summary of protocol deviations will be provided.

9.0 Study Drug Exposure and Compliance

Study drug exposure and compliance will be summarized using the mean, standard deviation, minimum, median, and maximum. Exposure to study drug will be summarized by treatment group.

Compliance is defined as the number of capsules taken (i.e., the difference between the number of capsules dispensed and the number of capsules returned) divided by the number of capsules a subject is supposed to take each day times the length of time that the subject was in the Treatment Phase of the study (i.e., Final/Discontinuation Visit date during Treatment Phase – Day 1 [Baseline] Visit date + 1). Subjects with missing data for the number of capsules returned will be excluded from the summary.

10.0 Efficacy Analysis

10.1 General Considerations

All statistical tests will be two-sided with the significance level of 0.05. Descriptive statistics will be provided. These include the number of observations, mean, standard deviation, minimum, median, and maximum for continuous variables; and number and percent for discrete variables. The analysis will be performed using SAS[®] (SAS Institute Inc., Cary, NC, USA).

Efficacy analyses will be performed based on ITT1A analysis set. The primary analysis and ranked secondary analysis will be repeated in the ITT1B analysis set and results will be reported separately in the final clinical study report.

Dose Response Modeling

Other than estimating the relative treatment effect of the investigational compound ABT-494 to placebo, one important goal of this Phase 2b substudy is to establish

dose-response relationship to facilitate the dose selection for Phase 3 substudies. Multiple Comparison Procedure and dose-response Modeling (MCP-Mod) with a pre-defined group of candidate dose response curves will be tested against flat dose-response curve to best characterize the dose-response relationship.

Steps of MCP-Mod:

1. Choose a candidate set of \mathcal{S} models.
2. Compute the optimum contrast for each model.
3. Use contrast test to find the significant T models while preserving FWER.
4. Use AIC criteria to find the most significant model from the significant T models found from Step 3.
5. Use the model found from Step 4 to fit observed data from the study and make inference (e.g., to find Minimum Effective Dose (MED) or the dose achieving certain amount of maximum effect), or use all significant models to make inference about the weighted target dose of interest.

ADDPLAN or R will be used to evaluate different dose-response models and to make dose recommendation.

10.2 Primary Efficacy Analyses

This section provides the details of the primary efficacy analysis for Substudy 1.

Primary Efficacy Endpoint:

Proportion of subjects who achieve clinical remission per Adapted Mayo score (defined as stool frequency subscore (SFS) ≤ 1 , rectal bleeding subscore (RBS) of 0, and endoscopic subscore ≤ 1) at Week 8.

Analysis Data Set for the Primary Efficacy Analysis:

The primary efficacy analysis will use the ITT1A analysis data set.

Imputation Method Used for the Primary Efficacy Analysis:

The primary efficacy analysis will use the NRI method to impute the missing values at Week 8 for Substudy 1.

Statistical Method of the Primary Efficacy Analysis:

The comparisons between an ABT-494 treatment group and placebo on the primary efficacy endpoint will be performed using MCP-Mod approach in the ITT1A analysis set.

The dose-response relationships among the four ABT-494 treatment groups and placebo group will be characterized for the primary endpoint at Week 8 using MCPMod approach. The following models will be considered: log-linear, E_{\max} , exponential, logistic and $\text{sig}E_{\max}$, Quadratic. The MCPMod approach for trial analysis stage consists of two main steps: MCP and Mod step. The MCP step focuses on establishing evidence for a drug effect across the doses, i.e., detecting a statistically significant dose response signal for the clinical endpoint and patient population investigated in the study. This step will typically be performed using an efficient test for trend, adjusting for the fact that multiple candidate dose response models are being considered. If a statistically significant dose response signal has been established at significance level of 0.05 using two-sided test, one proceeds with determining a reference set of significant dose response models by discarding the non-significant models from the initial candidate set.

The response function will be the log odds (logit) of the proportion of subjects with endoscopic/clinical remission. The fitted curve will be shown graphically with confidence intervals for each dose. Estimates of the treatment differences in the response function and associated 95% confidences for each active dose against placebo will be calculated from the model. These results will be back-transformed to give point estimates of the difference in proportions and associated 95% confidence intervals.

The pairwise comparisons for the difference in proportions of subjects between the treatment groups and placebo group will be performed using the Cochran-Mantel-Haenszel (CMH) test and will be stratified by previous biologic use, baseline corticosteroid use and baseline Adapted Mayo score (≤ 7 and > 7). Additionally, the CMH-based 95% confidence interval for the difference in proportions will be provided.

Sensitivity Analyses for the Primary Efficacy Endpoint:

- Hybrid multiple imputation method, as described in Section 6.0, will be to impute missing data.
- The last observation carried forward (LOCF) method will be used to impute missing data.
- Analysis of the primary endpoint will be conducted excluding the ITT1A subjects who did not meet inclusion/exclusion criteria.

As a sensitivity analysis, the clinical remission endpoint will also be summarized using the worst rectal bleeding subscore instead of the average rectal bleeding subscore. For this analysis, the rectal bleeding subscore will be calculated as the worst score during the most recent consecutive 3-day period prior to the study visit. If diary entries from the 3 consecutive days prior to the visit are not available, the worst value of the entries from the most recent 3 non-consecutive days will be utilized. If less than 3 days of diary data are available, rectal bleeding subscore will be considered missing.

In addition, an exploratory analysis of clinical remission at Week 8 will be conducted using the definition of stool frequency subscore (SFS) ≤ 1 , rectal bleeding subscore (RBS) of 0, and endoscopic subscore of 0.

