Since subjects do not always adhere to the study visit schedule, the following rules will be applied to assign actual visits to protocol-specified visits including early termination visits. For each study visit mentioned in the protocol, a nominal or target day will be selected to represent the corresponding visit along with a window around the target day. Windows will be selected in a non-overlapping fashion so that a date collected on the CRF does not correspond to multiple visit windows. Moreover, windows will not discard any Post-Baseline measurement recorded on the CRF. If a subject had two or more actual visits in one visit window, the visit closest to the schedule visit will be used as the study

visit for that window. If two visits are equidistant from the target, then the later visit will be used for reporting. If more than one assessment is collected on the same day, then the average of those assessments will be used in analyses.

Table 1. Visit Windows for Analysis of Partial Mayo Score, HCRU, Laboratory Parameters and Vital Signs for Substudy 1

Scheduled Week	Nominal Day	Time Window (Rx Day Range)
Week 0	1 ^a	≤ 1
Week 2	15	2 – 22
Week 4	29	23 – 36
Week 6	43	37 – 50
Week 8	57	51 – 71 ^b

Rx Day A = date of visit – date of first study drug in Substudy 1 + 1.

- a. Day of first dose of study drug in Substudy 1.
- b. Rx Day 71 or the date of the first dose of Substudy 3/Study M14-533, whichever is earlier.

Table 2. Visit Windows for Analysis of Mayo Score, ECG, Fasting Lipids and Lymphocyte Subset for Substudy 1

Scheduled Week	Nominal Day	Time Window (Rx Day Range)
Week 0	1 ^a	≤ 1
Week 8	57	2 – 71 ^b

Rx Day = date of visit – date of first study drug in Substudy 1 + 1.

- a. Day of first dose of study drug in Substudy 1.
- b. Rx Day 71 or the date of the first dose of Substudy 3/Study M14-533, whichever earlier.

Table 3. Visit Windows for Analysis of hs-CRP and Patient Questionnaires (IBDQ, SF-36, etc.) for Substudy 1

Scheduled Week	Nominal Day	Time Window (Rx Day Range)
Week 0	1 ^a	≤ 1
Week 2	15	2 – 22
Week 4	29	23 – 43
Week 8	57	44 – 71 ^b

Rx Day = date of visit – date of first study drug in Substudy 1 + 1.

- a. Day of first dose of study drug in Substudy 1.
- b. Rx Day 71 or the date of the first dose of Substudy 3/Study M14-533, whichever earlier.

Table 4. Visit Windows for Analysis of Fecal Calprotectin for Substudy 1

Scheduled Week	Nominal Day	Time Window (Rx Day Range)
Week 0	1 ^a	≤ 1
Week 2	15	2 – 36
Week 8	57	37 – 71 ^b

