Rx Day = date of visit – date of first study drug in Substudy 1 + 1.

- a. Day of first dose of study drug in Substudy 1.
- b. Rx Day 71 or the date of the first dose of Substudy 3/Study M14-533, whichever earlier.

Rules for Efficacy Assessment Based on Concomitant Treatment

Subjects in whom the maximum steroid dose exceeds the dose used at Baseline will be considered non-responders and will be censored for efficacy assessments (i.e., they will be considered non-responders for categorical endpoints and will have Baseline values carried forward for non-categorical assessments) from that point forward through the end of the study. These subjects will continue to be evaluated in the safety analysis set.

The equivalent steroid dose will be determined based on [Table 5](#):

Table 5. Equivalent Steroid Dose

Corticosteroid	Equivalent Dose (mg)
Cortisone	25
Hydrocortisone	20
Prednisone	5
Prednisolone	5
Triamcinolone	4.0
Methylprednisolone	4.0
Betamethasone	0.75
Dexamethasone	0.75
Budesonide	1
Beclomethasone	5

Subjects in whom the following UC-related medications (oral aminosalicylates, systemic corticosteroids, and MTX) that were not being taken at Baseline and are initiated during

the study or who have dosages of these medications increased to greater than the dose taken at Baseline will be censored for efficacy assessments (i.e., will be considered non-responders for categorical endpoints and will have the last values carried forward for non-categorical assessments) from that point through the end of the study. These subjects will continue to be evaluated in the safety analysis set.

Definition of Missing Data Imputation

The following imputation methods will be used to impute missing values in the efficacy analyses. In addition, an observed case analysis will be performed.

Non-Responder Imputation (NRI)

The NRI approach is used for binary efficacy variables. These variables can take values of 'Achieved' or 'Not Achieved' or may be missing for any reason including discontinuation from study. According to the NRI imputation approach, all missing values will be considered as 'Not Achieved.'

Last Observation Carried Forward (LOCF)

For all variables (categorical variables and continuous variables), the following rules will be used for the LOCF approach:

1. Baseline and Pre-Baseline values will not be used to impute the missing Post-Baseline values.

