2. Missing values after Study Day 1 will be imputed using the latest non-missing values after Day 1 and prior to the missing value. If there are no non-missing values after Baseline, then the LOCF value will be missing.

Hybrid Multiple Imputation Method

Primary endpoint of clinical remission will be analyzed using hybrid multiple imputation method. Subjects who discontinue prior to Week 8 due to lack of efficacy or AEs will be

considered as "not achieved" for clinical remission. Subjects who discontinue for other reasons will be categorized according to multiple imputations.

Mixed-Effect Model Repeated Measure (MMRM)

The MMRM model will be used for continuous efficacy variables with longitudinal data as the primary analysis. The MMRM model includes the baseline values as covariate; randomization stratification factors, treatment, time point and treatment-by-time point interaction as fixed effects; and subjects within treatment as random effect. An unstructured (co)variance structure will be used to model the within subject error. The comparison at a time point will be the contrast between treatments at that time point. Satterthwaite's approximation will be used to estimate denominator degrees of freedom.

Observed Case (OC)

Observed case analysis will be performed such that missing values will not be imputed.

Imputation of Missing Dates

For Baseline, efficacy, and safety parameters, if the day and/or month are missing, the following conventions will be used to impute the missing dates:

- 01 for missing start day
- End of month for missing end day
- January 1st for missing start month
- December 31st for missing end month

In case of partially missing AE start and stop dates, the dates will be imputed by comparing to first dose date of study medication so that the corresponding AEs will be made treatment-emergent whenever possible. If the start date of an AE is partially missing and the month is the same as the start date of a new therapy, the AE will be made treatment emergent to the new therapy.

In case of missing or partially missing study drug dosing dates, the dates will not be imputed. Subjects will be treated as not receiving dose on that date.

Rules for Calculation of Stool Frequency Subscore and Rectal Bleeding Subscore

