10.3 Secondary Efficacy Analyses

For the analysis purpose, the secondary efficacy endpoints are divided into two groups: (1) ranked secondary endpoints and (2) additional, non-ranked endpoints. The second group includes all other additional secondary variables. All analyses of secondary endpoints will be performed using the ITT1A analysis set of Substudy 1.

Ranked secondary efficacy variables (ranked hierarchically in decreasing order) for Substudy 1 are:

1. Proportion of subjects with endoscopic improvement (defined as an endoscopic subscore ≤ 1) at Week 8
2. Proportion of subjects achieving clinical remission per Full Mayo score (defined as a Full Mayo score ≤ 2 with no subscore > 1) at Week 8
3. Proportion of subjects achieving clinical response per Adapted Mayo score (defined as decrease from baseline in the Adapted Mayo score ≥ 2 points and $\geq 30\%$ from baseline, PLUS a decrease in rectal bleeding subscore (RBS) ≥ 1 or an absolute RBS ≤ 1) at Week 8
4. Proportion of subjects achieving clinical response per Partial Mayo score (using the Mayo Scoring System for Assessment of Ulcerative Colitis Activity, excluding endoscopic subscore; clinical response defined as decrease from baseline in the Partial Mayo score ≥ 2 points and $\geq 30\%$ from baseline, PLUS a decrease in rectal bleeding subscore (RBS) ≥ 1 or an absolute RBS ≤ 1) at Week 2
5. Change in Full Mayo score from Baseline to Week 8
6. Proportion of subjects with endoscopic remission (defined as an endoscopic subscore of 0) at Week 8
7. Proportion of subjects who achieved histologic improvement (defined as decrease from baseline in Geboes score) at Week 8

The additional, non-ranked endpoints include:

- Proportion of subjects who achieve clinical remission per Adapted Mayo score over time.
- Proportion of subjects achieving clinical remission per Partial Mayo score over time.

- Proportion of subjects achieving clinical remission defined as stool frequency subscore ≤ 1 , rectal bleeding subscore of 0, and endoscopic subscore ≤ 1 with absence of friability over time.
- Proportion of subjects achieving clinical remission defined as stool frequency subscore of 0, rectal bleeding subscore of 0, and endoscopic subscore of 0 over time.
- Proportion of subjects achieving clinical response per Partial Mayo score over time.
- Proportion of subjects with stool frequency subscore ≤ 1 over time.
- Proportion of subjects with rectal bleeding subscore of 0 over time.

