- Proportion of subjects with fecal calprotectin below 150 mg/kg over time.
- Proportion of subjects with IBDQ response (increase of IBDQ ≥ 16 from Baseline) over time.
- Change from Baseline in hs-CRP over time.
- Change from Baseline in fecal calprotectin over time
- Change from Baseline in Adapted Mayo score, Full Mayo score, Partial Mayo score and Mayo subscores over time.
- Change from Baseline in UCEIS score over time.
- Proportion of subjects with histologic remission (defined as Geboes score < 2) at Weeks 8 and 44.
- Change from Baseline in histologic score over time.
- Change from Baseline in laboratory and nutritional parameters (e.g., hemoglobin, hematocrit, albumin, total protein concentration, and weight).
- Change from Baseline in subject-reported stool frequency (absolute values).
- Change from Baseline in IBDQ score over time.
- Change from Baseline in EQ-5D-5L score over time.
- Change from Baseline in WPAI scores over time.
- Change from Baseline in SF-36 PCS, MCS components and domain scores over time.
- Change in PGIC score over time.

- Change from Baseline in FACIT-F score over time.
- Change from Baseline in UC-SQ score over time
- Health care resource utilization (UC-related hospitalizations and surgeries) during the study.

For categorical efficacy endpoints, the pairwise comparisons for the difference in proportions of subjects between treatment groups and placebo group will be analyzed using the CMH test adjusted for previous biologic use, baseline corticosteroid use and baseline Adapted Mayo score (≤ 7 and > 7). Additionally, the CMH based two-sided 95% confidence interval (CI) for the difference in the proportions between the treatment groups and placebo group will be provided.

The non-responder imputation will be used for subjects with missing data at the endpoint evaluated. The last observation carried forward (LOCF) method will also be used as the sensitivity analyses for the secondary endpoints.

Continuous secondary efficacy variables will be analyzed using an Analysis of Covariance (ANCOVA) model including factors for treatment group and stratification variables. Baseline values will be used as a covariate in the ANCOVA models.

Both last observation carried forward (LOCF) and observed case (OC) analyses will be used for continuous endpoints when conducting ANCOVA analysis. The LOCF analysis is considered primary for inferential purposes. HCRU will be analyzed as observed only.

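### Substudy 1's LOCF cannot impute a missing Week 8 endoscopy or biopsy, or a missing Week 2 Partial Mayo score, so its LOCF analyses of the primary and ranked endpoints are essentially observed-case

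*SAP*

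**What the plan says.** References are to the Substudy 1 SAP unless stated.

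Section 10.2 lists LOCF among the sensitivity analyses of the primary endpoint: "The last observation carried forward (LOCF) method will be used to impute missing data". Section 10.3 gives it the same role for the secondary endpoints, where non-responder imputation (NRI) is the main method for binary outcomes. For continuous endpoints it plans ANCOVA on both LOCF and observed-case data and adds: "The LOCF analysis is considered primary for inferential purposes". Only one ranked endpoint is continuous, number 5: "Change in Full Mayo score from Baseline to Week 8". Section 10.3 places all secondary analyses in ITT1A.

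Section 6.0 sets the LOCF rules:
- Scope: "For all variables (categorical variables and continuous variables), the following rules will be used for the LOCF approach".
- Source of the carried value: "Missing values after Study Day 1 will be imputed using the latest non-missing values after Day 1 and prior to the missing value".
- What is ruled out: "Baseline and Pre-Baseline values will not be used to impute the missing Post-Baseline values".
- With no source: "If there are no non-missing values after Baseline, then the LOCF value will be missing".

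The same section fixes the analysis windows. Table 2, "Visit Windows for Analysis of Mayo Score, ECG, Fasting Lipids and Lymphocyte Subset for Substudy 1", has one post-Baseline window, Week 8, covering Rx Days 2 to 71. Table 1 gives the Partial Mayo score windows at Weeks 2, 4, 6 and 8.

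Section 6.0 also has two concomitant-treatment rules. Subjects whose steroid dose rises above Baseline become non-responders on binary endpoints and keep their Baseline value on continuous ones. Subjects who start or increase certain UC medications become non-responders, or have their last value carried forward.

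**The concern.** LOCF can act only if an outcome has been read at least once after Baseline before the visit of interest. The Mayo score and histology in Substudy 1 are read once after Baseline, and ranked endpoint 4 is read at the first post-Baseline visit. If no earlier value exists, a sensitivity analysis named LOCF does not test the handling of missing data as its name suggests; it repeats the observed-case analysis.

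Ranked endpoint 5 matters more, because LOCF there is the inferential analysis and not a sensitivity check. If LOCF cannot fill the gap, ANCOVA has no outcome for the subject, and the result no longer rests on all of ITT1A. MMRM does not help: Section 10.3 reserves it for repeated measurements, and the Full Mayo score has only one after Baseline. The Protocol (Section 3.0) reports that the dose-response objective was met for all ranked secondary endpoints, so this endpoint was among those relied on. The documents do not say which analysis of it lay behind that statement.

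**Working it through.** No figure in the plan depends on LOCF, so there is none to reproduce. The only sizing figure for this substudy, 68% average power (Section 4.3), does not involve it. The check is a trace of the rules.

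**Inputs.** LOCF rules and windows: Section 6.0. Partial Mayo windows (Table 1): Week 2, Days 2–22; Week 4, Days 23–36; Week 6, Days 37–50; Week 8, Days 51–71. Mayo score window (Table 2): Week 8, Days 2–71. Histology has no window in these tables; the Protocol (Appendix C) schedules endoscopy with biopsy at Screening and Week 8 of induction. Endpoint components: Sections 4.5, 10.2 and 10.3.

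**Rule.** A usable source is a post-Baseline window that ends before the target window starts. The SAP does not say whether LOCF acts on the whole score or on its subscores, so both are traced.

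| Endpoint | Read at | Sources, whole score | Sources, by component |
|---|---|---|---|
| Primary; ranked 3 | Week 8 | none | SFS, RBS: Weeks 2, 4, 6; endoscopy: none |
| Ranked 2 and 5 | Week 8 | none | SFS, RBS, PGA: Weeks 2, 4, 6; endoscopy: none |
| Ranked 1 and 6 | Week 8 | none | endoscopy: none |
| Ranked 4 | Week 2 | none | SFS, RBS, PGA: none |
| Ranked 7 | Week 8 | none | Geboes: none |

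Ranked 1, 4, 6 and 7 cannot be imputed on either reading. The primary endpoint and ranked 2, 3 and 5 cannot be imputed when endoscopy is missing. Subscore-level LOCF could complete them only when endoscopy is present and SFS, RBS or (for ranked 2 and 5) PGA is missing at Week 8. For SFS and RBS that should be rare, since this SAP's diary rule needs only three days of entries and sets no look-back limit.

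**Binary endpoints, illustration.** If every missing subject leaves the denominator, an arm's LOCF rate is its NRI rate divided by (1 − m), where m is the missing fraction: 20% / 0.90 = 22.2% at 10% missing. Apply the planning rates (30% and 12%, Section 4.3) to observed subjects. The observed-case difference is 18.0 points whatever is missing. Under NRI it is:
- 5% missing in both groups: 0.30 × 0.95 − 0.12 × 0.95 = 17.1 points
- 5% active, 15% placebo: 0.30 × 0.95 − 0.12 × 0.85 = 18.3 points
- 10% in both: 0.30 × 0.90 − 0.12 × 0.90 = 16.2 points
- 10% active, 20% placebo: 0.30 × 0.90 − 0.12 × 0.80 = 17.4 points

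With four active groups and one placebo group of 50, these patterns lose between 200 × 0.05 + 50 × 0.05 = 12.5 and 200 × 0.10 + 50 × 0.20 = 30 of 250 subjects.

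**Ranked 5, illustration.** All values here are assumptions: observed subjects improve by 4.5 points (active) and 2.0 (placebo), and missing subjects do not change. The observed-case difference is 4.5 − 2.0 = 2.5.
- 15% active, 5% placebo missing: 0.85 × 4.5 − 0.95 × 2.0 = 1.925, so 2.5 is 0.575 too high (about 30%)
- 5% active, 20% placebo missing: 0.95 × 4.5 − 0.80 × 2.0 = 2.675, so 2.5 is 0.175 too low (about 7%)

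The sign depends on which group loses more subjects.

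**The case against.** **LOCF is not wholly inert.** A reader might infer that it never imputes anything for these eight endpoints. The text does not go that far: the rules apply to all variables, and subscore-level LOCF could fill a Week 8 SFS, RBS or PGA gap when endoscopy is available. This stands for the primary endpoint and ranked 2, 3 and 5.

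**Not everyone without a Week 8 score is lost.** A reader might also call ranked 5 a pure complete-case analysis. Two provisions prevent that. Any post-Baseline Mayo score on Days 2–71, including one from an early-termination visit, counts as Week 8. Subjects above their Baseline steroid dose keep a Baseline value. This too stands. The medication-change rule is less clear: it carries the last value forward, but before Week 8 the only Full Mayo value is Baseline, which the LOCF rules exclude.

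**The magnitudes are assumed.** The documents give no dropout rates or Full Mayo changes. The 30% figure needs more loss on active than on placebo, and its benchmark sets change to zero in missing subjects. Multiple imputation under missing-at-random does not target that quantity. This stands; the figures show possible directions only.

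**The effect on decisions is limited.** The primary and ranked binary analyses use NRI, hybrid multiple imputation is already planned for the primary endpoint, and an observed-case contrast with NRI is weak evidence but not worthless. LOCF does work for endpoints such as IBDQ, which has Week 2 and Week 4 windows (Table 3). Pairwise tests are at nominal level without multiplicity adjustment (Section 10.4), and Phase 2b data are not pooled with Phase 3 (Protocol Section 5.6.1). All this limits the importance of the point. It does not answer it for ranked 5, or for the ranked binary endpoints, where LOCF is the only imputation-based sensitivity method named.

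**Conclusion.** The point holds in limited form. Under the SAP's own rules and windows, a missing Week 8 endoscopic subscore, Week 8 Geboes score or Week 2 Partial Mayo score has nothing to be carried forward. The LOCF sensitivity analyses in Sections 10.2 and 10.3 are therefore essentially observed-case for the primary and ranked endpoints. The LOCF-ANCOVA named as inferential for ranked 5 leaves out ITT1A subjects who have no post-Baseline endoscopy on Days 2–71 and are not kept by a concomitant-treatment rule. That these subjects drop out is inferred from the value staying missing; the SAP does not say so outright.

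The documents do not support reading this as a flaw in the primary result, or as a demonstrated overstatement of the effect on ranked 5. Any bias there depends on how many subjects lack an endoscopy, in which groups, and how they fared, none of which the documents give. It should be corrected, but it does not disturb the NRI analyses.

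**What to change.** **Section 10.2.** Drop LOCF as a sensitivity analysis of the primary endpoint, keep hybrid multiple imputation, and label observed-case results as such.

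**Section 10.3, ranked 5.** Make the primary analysis an ANCOVA after multiple imputation of the Week 8 Full Mayo score, with treatment, stratification factors, Baseline and the Partial Mayo scores at Weeks 2, 4 and 6 in the imputation model. Keep the concomitant-treatment rules of Section 6.0, state what the last value is for a Full Mayo score under the medication-change rule, and use observed case as sensitivity.

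**Section 10.3, ranked binary endpoints.** Use hybrid multiple imputation in place of LOCF as the sensitivity analysis.

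**Reporting.** Substudy 1 is already unblinded, so label any re-run post hoc and describe LOCF results already reported for these endpoints as essentially observed-case.

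**Cost.** SAP wording and one re-run with methods the SAP already uses, on data already collected. The downside is one more imputation model, with its own missing-at-random assumption, for a Phase 2b endpoint.
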